1.2 Objectives

The primary goal of the multicenter PRAISE study is to develop a diagnostic algorithm to better identify ACS as origin of troponin elevation in patients with an acute ischemic stroke. The primary hypothesis will test whether dynamic troponin levels (as compared to stable ones) indicate presence of ACS. The following hypotheses will be tested:

Primary hypothesis: A dynamic troponin elevation (>50% change at measurement after 3 hours) indicates an ACS in patients with an acute ischemic stroke. The change in troponin level (dynamic vs. stable after 3 hours) within patients with an acute ischemic stroke can be used to differentiate whether an ACS is present.

Endpoint: diagnosis of “ACS”, determined by an independent endpoint adjudication committee.

1. Secondary hypothesis: Stroke patients with dynamic troponin change have a worse functional outcome three or twelve months after the event in comparison to those with stable troponin.

Endpoints: Modified Rankin-Scale (mRS) after three and twelve months.

2. Secondary hypothesis: Stroke patients with dynamic troponin change have an increased risk for recurrence of cardiovascular events and a higher mortality rate in comparison to those with stable troponin.

Endpoints: Brain infarcts, transient ischemic attack (TIA), myocardial infarction (MI) and death as well as the combined endpoint thereof (MACE) during the acute inpatient stay, after three and twelve months.

In addition, in an exploratory approach we want to establish a combined rule-in/rule-out diagnostic algorithm to identify the subgroup of troponin-positive stroke patients in whom the diagnosis of ACS (i.e. type I vs. type II MI) vs. not is made by means of coronary angiography including stroke-specific cut-off values for troponin and other biomarkers, the value of ECG, echocardiography, clinical parameters, and combinations thereof.

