4.5 Baseline patient characteristics

Baseline is defined as the measurement recorded at hospital admission (< 72 h after admission) (“V1”). All relevant characteristics to be measured at baseline are listed in table 1 of the study protocol (Nolte, et al. 2020)). Patients will be described with respect to

- Age
- Gender
- Medical history/comorbidities
 - o Diabetes mellitus
 - o Hypertension
 - o Hyperlipidemia
 - o History of coronary artery disease
 - o Heart failure
 - o Atrial fibrillation
 - o Previous history of stroke
 - o history of cancer
 - o smoking status
- acute therapy of ischemic stroke
 - o i.v. thrombolysis
 - o thrombectomy
- Physical examination
 - o Heart rate on admission
 - o systolic blood pressure on admission
 - o diastolic blood pressure on admission
- Current Medication
 - o Antiplatelet therapy
 - o dual antiplatelet therapy
 - o oral anticoagulation
 - o statin
 - o beta-blockers
- NIHSS
- mRS
- GRACE Score
- MoCA
- Creatinine
- Haemoglobin
- Peak troponin T

both overall and separately for presence/absence of dynamic troponin elevation and additionally for the presence/absence of ACS as well as for the diagnostic categories no ACS, MI Type 1 and MI type 2. Categorical data will be summarised by numbers and percentages. Continuous data will be summarised by mean, SD, median, IQR and range. Number of available observations and number of missing observations will be presented for the diagnostic groups (dynamic vs. stable) separately and overall for both groups. Differences in baseline variables between the two diagnostic groups will be analysed by appropriate tests, e.g. Chi-squared test, Mann-Whitney-U test, or analyses of variance.

5 Analysis

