5.1.2 Secondary endpoints

Secondary endpoint analysed are performed in an explorative manner without adjustment for multiplicity.

The secondary endpoints

- Mortality
- cardiovascular events (stroke, TIA, Myocardial infarction)
- MACE (combined endpoint of death, recurrent stroke, TIA, myocardial infarction)

are time-to event data. Event rates at 1 week, 3- and 12-months follow-up are reported based on Kaplan-Meier estimators. Cox proportional hazards will be used to estimate hazard ratios (95%-CI) comparing the diagnostic groups (stable vs. dynamic) for mortality and cause-specific hazard ratios for cardiovascular events taking death as competing event into account.

The secondary endpoint

- mRS (measured at baseline, 1 week, 3- and 12-months follow-up)

is an ordinal scaled score which ranges from 0 (no symptoms) to 6 (death). This endpoint will be analysed by fitting a proportional-odds logistic regression model to calculate the common odds ratio (95%-CI) as a measure of the likelihood that individuals in the stable group would lead to lower scores on the mRS scale than would patients in the dynamic group.

During the course of the study it turned out that the imaging procedure and count of hospital admission were not realisable. Therefore, these endpoints cannot be analysed.

Table 1 gives an overview of measurement time points of all endpoints.

Endpoints	Time point			
	V1 < 72 h after admission	V2 < day 7 days	V3 3-months FU	V4 12-months FU
Primary endpoint				
Acute coronary syndrome (ACS)			X	
Secondary endpoints				
Cardiovascular events (stroke, TIA, death, MI)			X	X
MACE (combined endpoint)		X	X	X
Mortality		X	X	X
mRS	X	X	X	X
MI Type 1 / MI Type 2			X	

Table 1: Frequency and scope of study visits

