5.3 Additional analyses

The primary outcome analysis is repeated in the PP population. Additional analyses of the presence/absence of ACS in relation to presence/absence of dynamic troponin elevation include the calculation of further diagnostic accuracy measures like sensitivity and specificity together with the 95%-confidence interval.

A mediation analysis will be conducted to identify direct and indirect effects of the diagnostic group (dynamic vs. stable) and additionally peak troponin T in patients with available troponin T values (exposure variables) and the presence of ACS (yes vs. no) as well as presence of MI type 1 (yes vs. no) and in patients with ACS MI (Type 1 vs. Type 2) (mediator variables) on mortality and MACE (target outcome) using accelerated failure time models. This will be performed after unblinding of the diagnostic groups and analysed in an explorative manner.

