5.3.2 Adjusted analyses

For the primary endpoint univariate and multiple logistic regression models will be fitted to the data to calculate unadjusted and adjusted odds ratios, including a series of baseline regressors:

- Age (continuous)
- Gender (dichotomous)
- Diabetes (dichotomous)
- Dyslipidemia (dichotomous)
- Renal failure (eGFR < 60 ml/min dichotomous)
- History of CHD (dichotomous)
- History of heart failure (dichotomous)
- History of atrial fibrillation/flutter (dichotomous)
- Haemoglobin (<12 g/dl for women, < 13 g/dl for men, dichotomous)
- Initial NIHSS (continuous)
- Heart rate (> 100/min, dichotomous)
- ECHO core lab: wall motion disturbance (dichotomous)
- ECG core lab findings: ACS typical changes (dichotomous)
- Peak troponin T value (continuous)

In an explorative analysis, an optimized multiple logistic regression model for the prediction of the primary endpoint is derived using the following procedure: in the first step, a multiple logistic regression model is established in a blinded manner, i.e. without taking troponin values into account, including relevant confounding variables into the model. In order to decide which variables are included in the model, clinical and statistical criteria are used, considering the distribution of the variables and their structure of missing values.

In the second step, variable selection is performed using backward selection.

In the last step, an unblinded analysis is performed, i.e. the troponin is included in the prognosis model to predict the primary endpoint. The final choice of variable selection method is based on the technical feasibility of the model, use of performance parameters, and clinical considerations. For the calculation of the ROC-AUC as performance measure, a 10-fold validation procedure will be performed.

The same procedure is applied in order to derive a prognostic model for the prediction of the presence of type 1 myocardial infarction as well as in those patients in whom ACS is present, for the prediction of type 1 vs. type 2 myocardial infarction as adjudicated by the EAC.

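### SAP 5.1.2 plans no covariate-adjusted companion to the exploratory dynamic-versus-stable comparisons of mortality, cardiovascular events and mRS, and states no group comparison for MACE

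*SAP*

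**What the plan says.** SAP 5.1.2 lists mortality, cardiovascular events and "MACE (combined endpoint of death, recurrent stroke, TIA, myocardial infarction" as time-to-event endpoints and promises Kaplan-Meier rates for them. The Cox models are then described as "comparing the diagnostic groups (stable vs. dynamic) for mortality and cause-specific hazard ratios for cardiovascular events taking death as competing event into account". MACE is not in that sentence. For mRS the method is "fitting a proportional-odds logistic regression model to calculate the common odds ratio". No covariate is named in any of these models. The section also states: "Secondary endpoint analysed are performed in an explorative manner without adjustment for multiplicity".

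Four other places bear on the point:

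- **SAP 5.3.2** lists 14 regressors, but the scope is set by "For the primary endpoint univariate and multiple logistic regression models will be fitted to the data". The later models in that section have infarction type as outcome. The protocol's statistical analysis section likewise limits adjusted odds ratios to ACS.
- **SAP 5.3** adds an exploratory step: "A mediation analysis will be conducted to identify direct and indirect effects of the diagnostic group (dynamic vs. stable". Its outcomes are mortality and MACE, fitted with accelerated failure time models. It names no baseline confounder and does not cover mRS.
- **SAP 4.5** says: "Differences in baseline variables between the two diagnostic groups will be analysed by appropriate tests". Nothing links the result to the outcome models of 5.1.2.
- **The protocol's sample size section** assigns secondary endpoints the same method as the primary one, an odds ratio by group, which is also unadjusted.

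**The concern.** A patient's group is set by how troponin moves over three hours, so the two groups need not be alike at baseline. The protocol's background says that troponin may rise through neurogenic injury from the stroke itself, or through chronic cardiac or extracardiac disease, and that a rise/fall pattern points to acute damage. It is a fair inference, though not something the documents state, that stroke features could push patients into the dynamic group, and age or chronic disease into the stable group. The two tendencies would work against each other, so the net direction is unknown.

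The entry rules narrow such differences but do not remove them. They exclude large infarcts, premorbid mRS above 3, life expectancy under one year and inability to consent.

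At stake is what can be said at the end. A reader shown a hazard ratio for dynamic troponin will ask whether it reflects more than older age, a worse stroke, earlier disability or known heart disease. Followed exactly, the plan gives no estimate that addresses this, although these variables are collected. If covariates are instead chosen after the baseline tests of SAP 4.5 have been seen, the choice is data-driven.

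**Working it through.** **Figures from the documents.** The plan gives no number for the secondary comparisons. Its sample size concerns the primary endpoint and serves here only to fix the group sizes. With stable risk 0.06 and odds ratio 4, the dynamic risk is 4×0.06/(0.94+4×0.06) = 0.203. The two-proportion formula with continuity correction (allocation 11:18, two-sided 5%, 80% power) gives 126 + 77 = 203, the protocol's figure. The dynamic group is 203×11/29 = 77.

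**Assumed inputs (not in the documents).** Effects on mRS: odds ratio 1.10 or 1.15 per NIHSS point, 1.03 per year of age, 1.4 per premorbid mRS point. Effects in Cox models: hazard ratio 1.05 or 1.10, 1.04 and 1.3 respectively. Imbalance: 1 NIHSS point, 2 years and 0.24 premorbid mRS points.

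**Approximate distortion with no true group effect.** The crude log ratio is roughly the sum of imbalance × log effect.

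- mRS terms: NIHSS ln 1.10 = 0.095 or ln 1.15 = 0.140; age 2×ln 1.03 = 0.059; premorbid mRS 0.24×ln 1.4 = 0.081.
- All three higher in the dynamic group: 0.235 to 0.280, so an odds ratio of 1.27 to 1.32.
- NIHSS alone: 1.10 to 1.15.
- NIHSS higher, age and premorbid mRS lower: 0.095 − 0.140 = −0.045, or 0.140 − 0.140 = 0, so an odds ratio of 0.96 to 1.00.
- Cox terms: 0.049 or 0.095; 2×ln 1.04 = 0.078; 0.24×ln 1.3 = 0.063. Aligned: 0.190 to 0.237, hazard ratio 1.21 to 1.27. Opposing: −0.093 to −0.046, hazard ratio 0.91 to 0.95.

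**Simulations (203 patients, 77 dynamic; NIHSS mean 4 SD 3 or mean 5 SD 5; mostly 1,500-2,000 trials per setting).**

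| Setting | Crude ratio | Rejection or power | Adjusted ratio | Rejection or power |
|---|---|---|---|---|
| mRS, null, aligned imbalance | 1.25-1.29 | 13-17% | 0.99-1.00 | 5-6% |
| mRS, null, 1 NIHSS point only | 1.09-1.15 | 6.1-8.9% | 0.99-1.00 | 4.9-6.7% |
| mRS, null, opposing imbalance | 0.97-1.01 | 3.6-5.2% | not run | not run |
| mRS, true OR 1.8, all three lower in the dynamic group | 1.34-1.43 | 22-30% | 1.81-1.84 | 61-63% |
| Cox, null, aligned, 20 to 50 events | 1.18-1.29 | 7-14% | 0.97-1.00 | 4-6% |

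The opposing row used 500 trials per setting, three NIHSS settings and a Wilcoxon test. For the true OR of 1.8, the crude model with balanced groups gave 1.68-1.75 and 53-60% power. The adjusted ratios near 1.00 show only that the models work when every confounder is in them, because the simulated confounders are exactly the ones adjusted for.

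**How many terms the data can carry.** With assumed 12-month event rates of 10, 15, 20 and 30%, 203 patients give 20, 30, 41 and 61 events. All 14 regressors of SAP 5.3.2 would leave 20/14 = 1.4 to 61/14 = 4.4 events each. Group plus three covariates leaves 20/4 = 5 to 61/4 = 15. The hazard ratio detectable with 80% power is exp[(1.960+0.842)/√(D×11/29×18/29)] for D events, that is 3.64, 2.87, 2.46 and 2.09.

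**The case against.** The strongest reply is that no stated aim is missed. The hypotheses are group comparisons; for mRS the SAP asks whether dynamic patients "have a worse functional outcome three or twelve months after the event in comparison to those with stable troponin". The protocol speaks of association, the analyses are labelled exploratory, and neither document claims independent prognostic value. This stands: the unadjusted ratios answer the question as worded.

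A second reply is that the MACE gap is mostly drafting. MACE is listed as time-to-event, has Kaplan-Meier rates and is modelled by group in SAP 5.3. That also stands in large part. A reader might infer that the SAP has no model of MACE by group at all; the mediation analysis shows otherwise. That analysis targets direct and indirect effects, however, and does not define a plain hazard ratio for the group contrast.

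A third reply is that the distortion depends on the direction assumed. This is right. The aligned setting is one possibility, and the mechanism inferred from the protocol points at least partly to opposing imbalances, which nearly cancel for mRS.

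A fourth is that few events limit adjustment. That argues against all 14 regressors, not against three.

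**Conclusion.** The gap in the text is real. Following the plan exactly yields only unadjusted contrasts for mortality, cardiovascular events and mRS, and no stated group comparison for MACE in SAP 5.1.2. The estimates are incomplete, not wrong.

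Two stronger readings are tempting and not supported. One is that the secondary analyses are invalid or biased by a known amount. The documents give no imbalance, covariate effect or event rate for these outcomes, so a null mRS odds ratio anywhere from about 1.0 to about 1.3 is compatible with the assumptions tried, and reversed imbalance could hide a true effect. The other is that an adjusted model would establish independent prognostic value. It would show only an association adjusted for the covariates it names.

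The primary analysis is not affected. This is a worthwhile, inexpensive improvement.

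**What to change.** Before outcome analysis, amend the SAP as follows.

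1. Keep the unadjusted estimates of 5.1.2. Add time to first MACE to the Cox sentence. In the same edit, reconcile SAP Table 1, whose cardiovascular-events row includes death, with the text, which treats death as competing.
2. Pre-specify companion Cox models (mortality, cause-specific cardiovascular events, first MACE) and proportional-odds models (mRS at 3 and 12 months) with group, age, admission NIHSS and premorbid mRS. Where events allow, add one cardiac-history term already collected, such as heart failure or coronary disease, because chronic cardiac disease is one of the reasons the groups may differ.
3. Fix a numeric event threshold and an order for dropping terms. As an illustration for the team to settle, ten events per model term would need 50 events for five terms, 40 for four and 30 for three, dropping cardiac history, then premorbid mRS, then age.
4. Use the same baseline confounders in the mediation models of 5.3.
5. Name premorbid mRS in 4.5, which lists only mRS, whereas protocol Table 1 has both. The imputation model of 5.2 draws its extra variables from 4.5.
6. Report results as adjusted for the named covariates.

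The cost is wording and a few models; no new data are needed. In the simulations the three-covariate Cox model raised the median standard error of the log hazard ratio from 0.46 to 0.47-0.48 at 20 events, from 0.37 to 0.38-0.39 at 30 and from 0.29 to 0.30 at 50. At 12 events it was 0.62 against 0.59, and estimates may be unstable. Dropping premorbid mRS left a hazard ratio of 1.02-1.07 where the truth was 1.

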5.2 Missing data

In case at least 5 % of the sample is missing, as a sensitivity analysis a multiple imputation is carried out in the mITD population to investigate the effects of missing values on the results of the primary and secondary analyses. To set up a proper imputation model, we will follow the recommendations of White, Royston and Wood (White IR 2011). The imputation model will include all outcome parameter variables (secondary endpoints) at baseline and all further available time points as well as further variables for model refinement (as defined in 4.5). The number of imputations will be defined by the percentage of missing values in at least one of those defined variables at all time points.

Further sensitivity analyses for the primary endpoint will be conducted using other mechanisms for replacement of missing values (e.g. best/worst case).

5.3 Additional analyses

The primary outcome analysis is repeated in the PP population. Additional analyses of the presence/absence of ACS in relation to presence/absence of dynamic troponin elevation include the calculation of further diagnostic accuracy measures like sensitivity and specificity together with the 95%-confidence interval.

A mediation analysis will be conducted to identify direct and indirect effects of the diagnostic group (dynamic vs. stable) and additionally peak troponin T in patients with available troponin T values (exposure variables) and the presence of ACS (yes vs. no) as well as presence of MI type 1 (yes vs. no) and in patients with ACS MI (Type 1 vs. Type 2) (mediator variables) on mortality and MACE (target outcome) using accelerated failure time models. This will be performed after unblinding of the diagnostic groups and analysed in an explorative manner.

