All patients included in the study will undergo coronary angiography, which is the gold standard to diagnose a coronary culprit lesion. The timing of coronary angiography will be determined according to the ESC guideline recommendations on risk stratification²⁸. Coronary angiography will be performed according to a SOP. Treating cardiologists may choose the cardiac catheter for coronary angiography. We will collect data on duration of the procedure, amount of contrast agent given, puncture site (radial vs. femoral), periprocedural anticoagulation, balloon dilatation and stent angioplasty. In addition, we will collect data on periprocedural complications, e.g. dissections, arrhythmias, thrombus formation, perforation, cardiac tamponade and type 4a myocardial infarction. For central reading in the core laboratory, imaging data will be uploaded via the imaging data management system (BDMS) of the DZHK. Coronary lesions will be evaluated regarding their localization and morphology according to the AHA classification.

Echocardiography:

Transthoracic echocardiography (TTE) will be performed by a cardiologist at the participating study site according to DZHK-SOP-K-08²⁹. For central reading in the core laboratory, imaging data will be uploaded via the imaging data management system (BDMS) of the DZHK.

Troponin:

Acute ischemic stroke patients with elevation of troponin values according to the inclusion criteria (see above) will be eligible for inclusion into the PRAISE study. Troponin will be measured on admission and after three hours during clinical routine in all recruiting study sites. A dynamic elevation of troponin is defined as a 20% change of troponin values in serial measurement with at least one value elevated above the assay-specific upper reference limit. Since not all recruiting study sites will use the same assay for measuring troponin in clinical routine, troponin will also be measured at a central core laboratory located at the University Hospital Hamburg-Eppendorf ([name]). At the core laboratory, high-sensitivity (hs)-Troponin-T will be measured using the Roche Elecsys-Assay and hs-Troponin I will be measured using the Siemens Architect-Assay.

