Troponin (0 und 3 h)	X			
Clinical chemistry	X			
DZHK-Biobanking (optional)		X		
Study-specific examinations				
GRACE-Score	X			
Adverse Events	X	X	X	X
ECG	X	X		
Echocardiography (TTE)		X		
Coronary angiography		X		
endpoints				
Acute coronary syndrome (ACS)		X		
Recurrent cerebral ischemia, myocardial infarction, mortality		X	X	X

Table 1: PRAISE study procedures

Statistical analysis:

Sample size calculation:

The sample size calculation of the PRAISE study is based on data from the TRELAS study (Troponin elevation in acute stroke)⁹. In the TRELAS study, 7/29 (24%) of ischemic stroke patients with troponin elevation had a coronary culprit lesion and 11/29 (38%) of patients had dynamic troponin elevation (i.e. Δ change $> 50\%$). Of 11 patients with dynamic troponin elevation, 6 patients (54%) had a coronary culprit lesion. In patients without dynamic troponin elevation, only one patient (1/18=6%) had a coronary culprit lesion. Thus, the odds ratio of a dynamic troponin elevation for presence of a coronary culprit lesion was at 20.4. Due to the small sample size of the TRELAS study, we used the lower limit of the 80% confidence interval of the odds ratio (~4) to calculate the sample size for the PRAISE study. We assumed that the proportion of stroke patients with dynamic troponin elevation will be similar to the TRELAS study. Thus, 203 patients will have to be included to achieve a statistically significant result with a power of 80% (alpha=0.05). Since the TRELAS study only recruited patients with an initial hs-troponin T value > 50 ng/l (Roche Elecsys Assay), the proportion of patients with dynamic troponin elevation will likely be even higher in PRAISE. In order to compensate for cases of withdrawal of consent we plan to include 251 patients. The primary hypothesis will be tested using an intention-to-diagnose analysis by calculation of the odds ratio of acute coronary syndrome in patients with dynamic vs. stable troponin elevation. Secondary endpoints will be analyzed using the same statistical method.

In order to assess other predictors of acute coronary syndrome we will use the Chi-Square-test for dichotomous variables and the Wilcoxon-Test for continuous variables.

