3.1 Confidence intervals and *P* values

All applicable statistical tests will be two-sided and will be performed using a 5% significance level. Analyses of secondary outcomes will be performed without adjustment for multiplicity. All confidence intervals presented will be 95% and two-sided.

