3.2 Adherence and protocol deviations

Adherence is not relevant in this study, since there is no therapeutic intervention for study purposes to be followed.

All protocol violations will be documented and classified as major or minor in a blinded manner by an independent staff member who is not involved in the study process.

A major protocol deviation occurs if contrary to the study protocol a patient could not receive a coronary angiography. The following reasons are listed:

- Data from coronary angiography are not provided for technical reasons.
- Patient refuses coronary angiography.
- Clinician declines coronary angiography for medical reasons.
- Coronary angiography is not performed for capacity reasons.
- A transfer of images from the ultrasound scanner is not possible for technical reasons.

Further, a major protocol deviation occurs if a troponin measurement is not available.

These patients will not be taken into regard into the primary analysis.

A minor protocol deviation occurs if a patient could not receive echocardiography. The following reasons are listed:

- Based on clinical indication, a transesophageal echocardiography is performed, which is not relevant for the objective of this trial.
- Echocardiography is not performed for capacity reasons.

Patients with minor protocol deviations are included in the primary analysis.

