3.3.2 Per Protocol population (PP)

The Per Protocol population includes all patients who have no major protocol violation. In particular coronary angiography must have been performed.

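### Sensitivity and specificity in SAP 5.3 have no stated population and no correction for missed angiography, so they will be biased if completion differs between dynamic and stable patients

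*SAP*

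**What the plan says.** SAP 5.3 repeats the primary analysis in the per-protocol (PP) population and adds "further diagnostic accuracy measures like sensitivity and specificity together with the 95%-confidence interval". No population is attached to the added measures.

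For PP, SAP 3.3.2 says: "In particular coronary angiography must have been performed". The modified intention-to-diagnose (mITD) population in SAP 3.3.1 asks only for both troponin values.

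Protocol (Coronary angiography) and SAP 2.2 have every patient undergo angiography. SAP 3.2 nevertheless lists why it may be absent: refusal by the patient, a clinician's medical decision, technical loss of data, and "Coronary angiography is not performed for capacity reasons".

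Troponin at 0 and 3 hours is measured in routine care at the sites (protocol, Troponin). On scheduling, the protocol says: "The timing of coronary angiography will be determined according to the ESC guideline recommendations on risk stratification".

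SAP 5.2 plans multiple imputation in mITD, as a sensitivity analysis for the primary and secondary analyses, when at least 5% of the sample is missing. It adds best/worst-case replacement for the primary endpoint. The endpoint committee is blinded to troponin and uses angiography, ECG, echocardiography and symptoms.

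**The concern.** An accuracy estimate restricted to patients who had angiography represents the whole cohort only if having it is unrelated to the index test. Here the people deciding about angiography have seen the index test. The protocol's Background also says that clinicians are often reluctant to perform angiography after stroke. Different completion in the two troponin groups is therefore plausible, though the documents do not show it.

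What is at stake is the pair of figures a clinician would take from the study. The planned PP repeat of the odds ratio gives no warning, because that ratio is unchanged by selection on troponin group alone.

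In mITD the problem takes another form. If patients without an angiogram stay in and the committee labels them, the label rests on ECG, echocardiography and symptoms. The protocol says stroke patients with ACS often lack chest pain, and SAP 3.2 allows echocardiography to be missing. Such a label counts as observed, so the imputation in SAP 5.2 would not touch it.

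**Working it through.** **The plan's own figure.** The documents state no sensitivity, specificity or completion rate. The only related figure is the sample size of 203. Inputs from the protocol (Sample size calculation) are an odds ratio of about 4, a stable-group rate written as 6%, 11 of 29 dynamic, 80% power and alpha 0.05 (two-sided by SAP 3.1).

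- Dynamic rate: 4 × 0.06 / (0.94 + 4 × 0.06) = 0.2034.
- The two-proportion formula with allocation 11:18 gives 108 stable patients; with continuity correction, 126. Dynamic: 126 × 11/18 = 77. Total 203, as stated.
- Loss allowance: 1 − 203/251 = 19.1%.

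**Starting accuracy.** The sample-size inputs imply an ACS rate of (18 × 0.06 + 11 × 0.2034)/29 = 11.4%, against the 24% (7/29) the protocol reports from the pilot. I therefore use two cases tied to 24%.

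- *Design case* (odds ratio 4, prevalence 7/29, 11/29 dynamic). With p0 the stable rate, 18·p0 + 11·4·p0/(1 + 3·p0) = 7. Hence p0 = 14.4% and the dynamic rate p1 = 40.1%. Sensitivity = 11 × 0.4014/7 = 63.1%; specificity = 18 × 0.8564/22 = 70.1%.
- *Pilot table at face value.* The protocol reports: "Of 11 patients with dynamic troponin elevation, 6 patients (54%) had a coronary culprit lesion". In the stable group it was 1 of 18. Sensitivity = 6/7 = 85.7%; specificity = 17/22 = 77.3%.

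**Effect of unequal completion.** Let r = completion in dynamic / completion in stable, and suppose completion depends only on troponin group. Then

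- PP sensitivity = r·Se / (r·Se + 1 − Se)
- PP specificity = Sp / (Sp + r·(1 − Sp))

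For 95% against 85%, r = 1.1176. In the design case sensitivity is 0.7050/(0.7050 + 0.3692) = 65.6% and specificity is 0.7007/(0.7007 + 0.3345) = 67.7%.

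All completion rates below are assumed. Shifts in points were taken before rounding.

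| Dynamic / stable completion | Design Se | Design Sp | Pilot Se | Pilot Sp |
|---|---|---|---|---|
| equal | 63.1 | 70.1 | 85.7 | 77.3 |
| 95 / 90 | 64.3 (+1.3) | 68.9 (−1.1) | 86.4 (+0.6) | 76.3 (−1.0) |
| 95 / 85 | 65.6 (+2.6) | 67.7 (−2.4) | 87.0 (+1.3) | 75.3 (−2.0) |
| 95 / 75 | 68.4 (+5.3) | 64.9 (−5.2) | 88.4 (+2.7) | 72.9 (−4.4) |
| 100 / 70 | 70.9 (+7.9) | 62.1 (−8.0) | 89.6 (+3.8) | 70.4 (−6.9) |
| 70 / 100 (reversed) | 54.5 (−8.6) | 77.0 (+6.9) | 80.8 (−4.9) | 82.9 (+5.7) |

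**Odds ratio.** It equals Se·Sp / [(1 − Se)(1 − Sp)]. The factor r cancels, so it stays at 4.0 (design) or 20.4 (pilot) in every row.

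**Does the correction work?** Take overall completion of 203/251 = 81%, split as 90% dynamic and 75.3% stable. Design-case raw PP values are 67.1% and 66.2%. Weighting each group by the inverse of its completion rate (the Begg-Greenes estimate) returns 63.1% and 70.1%.

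**Does SAP 5.2 cover it?** It names primary and secondary analyses, whereas these measures are additional ones. Its imputation model uses the secondary endpoints and the variables of SAP 4.5. Neither list names ACS, dynamic status or ECG findings.

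**The case against.** The strongest objection concerns direction. A reader might infer from the protocol's reference to risk stratification that stable patients will be skipped. That sentence governs when angiography is done, not whether. Capacity, technical failure and refusal have no stated link to troponin, and a clinician's refusal could fall on either group. Stable here means a change of 50% or less, and entry still required a highly abnormal first value or a change above 20%. This stands: the direction is conditional.

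Size is also open. A reader might take a shift of 2 to 8 points as a consequence of the plan. It corresponds to an assumed 10 to 30 point gap in completion; a 5-point gap gives about 1 point. With 203 × 7/29 = 49 ACS cases, the 95% half-width for sensitivity is about 10 to 14 points, wider than any shift shown. That lowers the priority. The interval does not, however, reflect a systematic shift.

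Angiography is the gold standard for a culprit lesion, whereas ACS is a committee diagnosis from several sources. This is true, but the algebra needs only that entry into PP depends on troponin group.

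It would be too strong to say the SAP ignores missing data. SAP 5.2 plans imputation and best/worst-case replacement, but neither is stated to apply to sensitivity and specificity, and neither reaches a patient who already has a label.

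Finally, the mITD part depends on an unresolved conflict. SAP 3.2 removes patients without angiography from the primary analysis, while SAP 3.3.1 keeps them. If 3.2 governs, the mITD part falls away.

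**Conclusion.** The gap holds as a conditional point about an additional analysis. SAP 5.3 leaves the population open and specifies no correction, and complete-case sensitivity and specificity are biased whenever completion differs by troponin group. With an odds ratio of 4 and 24% prevalence, the shift is about 1, 2.5, 5 and 8 points for gaps of 5, 10, 20 and 30 points. With the pilot table and stable patients the less often verified, sensitivity rises by at most about 4 points and specificity falls by up to about 7.

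These figures assume that completion depends only on troponin group. If it also depends on ECG findings, symptoms or frailty, size and direction can differ.

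Two stronger conclusions are not supported. A reader might infer that the PP odds ratio is biased too; under this assumption it is not. A reader might also infer that the mITD odds ratio is inflated because patients without an angiogram would be called free of ACS; no section says how the committee labels them. The point is worth acting on because the remedy is cheap and uses data already collected.

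**What to change.** In SAP 5.3:

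1. Name the population for sensitivity and specificity, after reconciling SAP 3.2 with 3.3.1.
2. Tabulate angiography completion by dynamic and stable status. The planned STARD flow diagram is a natural place for this.
3. Beside the raw values, report Begg-Greenes or inverse-probability-weighted sensitivity and specificity, using dynamic status, 0 h troponin, ECG findings and eGFR.
4. If patients without an angiogram remain in mITD, add a sensitivity analysis that treats their ACS status as missing, with ACS and dynamic status in the imputation model.

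The cost is SAP wording and a short extra analysis, with no new data. Intervals become slightly wider, and the corrected values rely on angiography being missing at random given the variables used. Keeping the raw values alongside lets the reader see how much the correction matters.
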